16.4. Safety Objective

Safety assessments include reported adverse events, laboratory tests results, and vital signs.

The profiles of adverse events for the arms with regard to incidences of treatment emergent adverse events will be assessed. Treatment emergent adverse events are defined as those events that appear during treatment or are present before treatment and subsequently worsen.

Laboratory, vital signs, and adverse event data will primarily be assessed for clinical safety. Data will be listed and summarized for each treatment according to measurement time.

Adverse events will be coded using the MedDRA dictionary. Coding includes system organ class (SOC) and preferred term (PT). All verbatim descriptions and coded terms will be listed for all AEs.

Safety summaries are described in the SAP.

17. REGULATORY AND ETHICS CONSIDERATIONS

17.1. Institutional Review Board (IRB)

This study protocol must be submitted to an IRB for review and approval prior to initiation. As this study will be conducted at multiple sites, it is expected that each site must submit and obtain approval from their designated IRB with preference towards use of a central IRB when at all possible. Before the investigational product can be shipped to the investigative site and before the consenting and screening of subjects at the site, the protocol, any protocol amendments, the consent form, any advertising materials, any materials to be provided to the subjects for the proposed clinical study, and any other documents required by the IRB must be submitted by the Investigator for review and approval by the IRB. The Investigator must also ensure that the IRB reviews the progress of the study, if necessary, and renews its approval of the study (if ongoing) on an annual basis. Any member of the IRB who is directly affiliated with this study as an Investigator or as site personnel must abstain from the IRB vote on the approval of the protocol and associated documents.

All amendments or revisions to the protocol must undergo review by appropriate IRBs. Amendments/revisions will be circulated to all participating sites with clear instructions regarding IRB review. Amendments will be submitted by the Sponsor to the FDA prior to central implementation to the study, and by IRBs prior to local implementation, EXCEPT when the amendment eliminates an immediate hazard to clinical trial subjects or is of a purely administrative nature.

A copy of the IRB approval letter must be forwarded to the Sponsor or Sponsor's representative before the study is implemented. The approval letter must clearly state the protocol title and version that was reviewed, as well as any associated documents. The Investigator also must forward copies of subsequent amendment approval letters to the Sponsor upon receipt.

17.2. Ethical Conduct of the Study

This trial will be conducted in accordance with the Declaration of Helsinki, as well as the ICH Guidelines on GCP, the US Code of Federal Regulations, and local requirements regarding IRB committee review, informed consent, and other statutes or regulations regarding the protection of the rights and welfare of human subjects participating in biomedical research.

17.3. Informed Consent

The informed consent forms used for the study must comply with the Declaration of Helsinki and its updates and the International Conference on Harmonization (ICH) Guidelines and must have been approved by the Sponsor or Sponsor's representatives (prior to review by the site's IRB) and the Investigator's IRB. The Investigator or an authorized associate, who must be a physician, must explain the nature of the study and the treatment in such a manner that the subject is aware of his/her rights and responsibilities, as well as potential benefits and risks. The Investigator is also responsible for answering any questions the subject may have throughout the study and sharing any new information, in a timely manner, that may be relevant to the subject's willingness to continue his/her participation in the trial.

Subjects must also be informed that participation is voluntary and that they may withdraw from the study at any time, without prejudice to their current or future care. Documentation of the discussion and the date of informed consent should be recorded in the subject's medical record or a study/clinic chart. Once all of their questions have been answered and they have voluntarily agreed to participate in the study, subjects will be asked to sign and date the Informed Consent Form.

Subjects, or their legally authorized representatives, must give informed consent in writing prior to the performance of any protocol-specific procedure. Subjects who cannot give informed consent (i.e. mentally incompetent subjects or those physically incapacitated such as comatose subjects) are not to be recruited into the study. Subjects who are competent but physically unable to sign the consent form may have the document signed by their nearest relative or legal guardian. A copy of the signed Informed Consent Form will be provided to the subject.

17.4. Subject Confidentiality

The Investigator must attempt to assure that the subject's confidentiality will be maintained within the limit of the law. Subjects will be identified by subject number and initials (or other code) on all documents submitted to the Sponsor. Subjects will not be identified by name.

All records will be kept in a secure place in the clinical research site. Computer data entry and data review programs will be done using subject numbers and initials (or other code) only. Clinical information will not be released without written permission of the subject, as outlined in the subject consent form.

The Investigator must maintain a log of subject names and identification codes.

18. DOCUMENTATION

18.1. Study File and Site Documents

Prior to the activation of the study, at a minimum, the following items must be received by the Sponsor from the site:

1. Confidential Disclosure Agreement.
2. Signed protocol, and amendment(s) page(s).
3. The Principal Investigator's curriculum vitae and current medical license. Note: Principal Investigator or a Co-Investigator must be a medical doctor (MD).
4. Documentation of required training for designated smoking cessation behavioral counselors.
5. Signed Clinical Study Agreement.
6. Signed Financial Disclosure Form from the relevant site personnel.
7. IRB written approval for the protocol, amendment(s), Informed Consent Form, Smoking cessation information and advertisements (if applicable).
8. IRB Membership list or an official statement from the IRB stating the IRB is in compliance with Good Clinical Practice (GCP).
9. FDA Form 1572.

18.2. Study Documents Supplied by the Sponsor

The Sponsor will supply the investigator with the following items:

1. Current version of the Investigator's Brochure.
2. Current version of study protocol.
3. Master CRF.
4. Informed Consent Form template.
5. Study Procedure Manual.
6. Laboratory Manual (if applicable).

18.3. Maintenance and Retention of Records

It is the responsibility of the investigator to maintain a comprehensive and centralized filing system of all relevant documentation.

Investigators will be instructed to retain all study records required by the Sponsor and regulatory authorities in a secure and safe facility with limited access for one of the following time periods based on notification from the Sponsor:

1. For a period of at least 2 years from the **last** marketing approval worldwide.
2. Or a period of at least two years after discontinuation of clinical development of the investigational product as confirmed by the Sponsor.

The investigator will be instructed to consult with the Sponsor before disposal of any study records and to provide written notification to the Sponsor of any change in the location, disposition, or custody of the study files.

19. ADMINISTRATIVE PROCEDURES

19.1. Sponsor Responsibilities

The study will be monitored by representatives of the Sponsor and/or designated contract research organizations (CROs). Routine monitoring visits will be conducted to (at a minimum):

1. Assure compliance with the study protocol.
2. Verify that the research facilities, including laboratories and equipment, are adequate to safely and properly conduct the study.
3. Verify that the investigational product is stored properly and under the proper conditions, is in sufficient supply, and that receipt, use, and destruction or return of investigational product at the study sites are controlled and documented adequately.
4. Verify that written informed consent was obtained before any protocol-specific screening procedures are performed solely for the purpose of determining eligibility for the clinical study and/or prior to the provision of study drug.
5. Review the subject CRFs and source documents to ensure that reported study data are accurate, complete, and verifiable from source documents.
6. Verify that the Investigator and study site personnel are adequately qualified throughout the study.
7. Verify that the safety information and amendments are submitted to the IRBs.

19.2. Investigator Responsibilities

All requested study data must be entered on the CRFs for the study. An explanation should be provided for all missing data. Correction of data on a CRF will be made with identification of the individual making the correction and date of the correction. Only individuals who are identified on the Delegation of Responsibility Form(s) may correct data on the CRF. For those subjects who withdraw before completion of their specified treatment schedule, all available efficacy and safety data must be entered in the CRF. The reason for withdrawal must be specified. Incomplete or inconsistent data on the CRFs will result in data queries that will be returned to the Investigator for resolution.

The Investigator must maintain adequate and accurate source documents upon which CRFs for each subject are based. The source documents are to be separate and distinct from the CRFs, except for cases in which the Sponsor has predetermined that direct entry into specified pages of the subject's CRF is appropriate. The documents to be maintained must include, but are not limited to, detailed notes on:

1. The medical history prior to participation in the study.
2. The basic identifying information, such as demographics, that link the subject's source documents with the CRFs.

3. The results of all diagnostic tests performed, diagnoses made, therapy provided, and any other data on the condition of the subject.
4. The subject's exposure to study treatment.
5. All AEs.
6. The subject's exposure to any concomitant therapy, including dates of administration.
7. All relevant observations and data on the condition of the subject throughout the study.
8. The oral and written communication with the subject regarding the study treatment, including the risks and benefits of the study. The date of informed consent must be recorded in the source documentation.

19.3. Regulatory Compliance

Quality Assurance representatives from the Sponsor or their delegate, and the FDA as required will be allowed to periodically visit the Investigators to discuss the conduct of the trial and, upon request, to inspect the records of the trial. These reviews are necessary to ensure that the study is conducted according to standards consistent with the ICH GCP Guidelines.

The Investigator agrees to discuss and correct, if necessary, any problems or deficiencies that are found during the course of these reviews.

19.4. Protocol Modification/Premature Termination

All protocol amendments must be written and approved by the Sponsor. Each IRB will review and approve amendments prior to their implementation in the study. IRB approval need not be obtained prior to removal of an immediate hazard to subjects.

The Sponsor may suspend or terminate the protocol early if safety or other issues occur. Furthermore, the study may also be terminated prematurely by the Sponsor for important corporate reasons, or due to instruction of the FDA due to safety reasons.

The Principal Investigator may terminate participation at his/her site at any time but must provide all study data for subjects randomized.

Following a decision of temporary suspension or discontinuation, it is a responsibility of the Principal Investigator to inform the study subjects and IRB stating the reasons for premature termination. The Sponsor shall be responsible for expedited reporting and/or notification to the FDA, as applicable.

19.5. Policy for Publication and Data Presentation

The Sponsor encourages the scientific publication of data from clinical research trials. However, Investigators may not present or publish partial or complete study results individually. The Principal Investigators and the Sponsor may propose appropriate scientific manuscripts or abstracts from the study data. Any manuscript or abstract proposed by the Investigators must be reviewed to ensure accuracy of data represented and commented upon in writing by the Sponsor prior to submission for publication. Investigators agree to consider the comments of the Sponsor in good faith and the Sponsor agrees in good faith not to impose limitations on access to the complete study data or unreasonable or inappropriate restrictions on publication of the study results. In case of publication, confidentiality of the study volunteers will be maintained.

Protocol No. ACH-CYT-09

APPENDIX 1. SUICIDAL BEHAVIORS QUESTIONNAIRE-REVISED (SBQ-R)

The Suicidal Behaviors Questionnaire-Revised (SBQ-R)¹⁷ provides a broad range of information in a brief administration. Responses can be used to identify at-risk individuals and specific risk behaviors. This questionnaire must be completed by all potential study subjects during screening. A score ≥ 7 indicates potential for suicidal ideation and would confirm study exclusion criteria #8.

This questionnaire must also be completed by all study subjects at the Day 27 (End of Treatment) and Week 8 clinic visits to monitor for any potential suicidal ideation or behaviour during the study as a safety parameter. An SBQ-R score ≥ 7 will be used to identify at-risk individuals who will need immediate evaluation by site personnel for any potential suicidal ideation. Any potential suicidal ideation or behavior will be considered an SAE.

Copies of this questionnaire and details for interpretation and scoring will be provided in the study Procedure Manual and completed questionnaires must be present as source documents. Any subject meeting this exclusion must be followed by the clinical site according to site policies.

1. **Have you ever thought about or attempted to kill yourself?** (check one only)
 - 1. Never
 - 2. It was just a brief passing thought
 - 3a. I have had a plan at least once to kill myself but did not try to do it
 - 3b. I have had a plan at least once to kill myself and really wanted to die
 - 4a. I have attempted to kill myself, but did not want to die
 - 4b. I have attempted to kill myself, and really hoped to die
2. **How often have you thought about killing yourself in the past year?** (check one only)
 - 1. Never
 - 2. Rarely (1 time)
 - 3. Sometimes (2 times)
 - 4. Often (3-4 times)
 - 5. Very Often (5 or more times)
3. **Have you ever told someone that you were going to commit suicide, or that you might do it?** (check one only)
 - 1. No
 - 2a. Yes, at one time, but did not really want to die
 - 2b. Yes, at one time, and really wanted to die
 - 3a. Yes, more than once, but did not want to do it
 - 3b. Yes, more than once, and really wanted to do it
4. **How likely is it that you will attempt suicide someday?** (check one only)
 - 0. Never
 - 1. No chance at all
 - 2. Rather unlikely
 - 3. Unlikely
 - 4. Likely
 - 5. Rather likely
 - 6. Very likely

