8.2. Exclusion Criteria

Subjects meeting ANY of the following exclusion criteria will NOT be eligible for inclusion into the study.

1. Known hypersensitivity to cytisine or any of the excipients.
2. Positive urinary drugs of abuse screen, determined within 28 days before the first dose of cytisine.
3. Clinically significant abnormal serum chemistry or hematology values within 28 days of randomization (i.e. requiring treatment).
4. Clinically significant abnormalities in 12-lead ECG determined after minimum of 5 minutes in supine position within 28 days of randomization (i.e. requiring treatment or further assessment).

5. BMI classification for being underweight ($<18.5 \text{ kg/m}^2$) or having \geq Class 2 obesity ($\geq 35 \text{ kg/m}^2$).
6. Recent history (within 3 months) of acute myocardial infarction, unstable angina, stroke, cerebrovascular incident or hospitalization for congestive heart failure.
7. Current uncontrolled hypertension (blood pressure $\geq 160/100 \text{ mmHg}$).
8. Documented diagnosis of schizophrenia or bipolar psychiatric illness; currently psychotic; having suicidal ideation (SBQ-R score ≥ 7); or current symptoms of moderate to severe depression (HAD score ≥ 11).
9. Renal impairment defined as a creatinine clearance (CrCl) $<60 \text{ mL/min}$ (estimated with the Cockcroft-Gault equation) or hepatic impairment defined as alanine aminotransferase (ALT) or aspartate aminotransferase (AST) $>2.0 \times$ the upper limit of normal (ULN).
10. Women who are pregnant or breast-feeding.
11. Male or Female subjects of child bearing potential who do not agree to use acceptable methods of birth control during the study treatment period.
12. Participation in a clinical study with an investigational drug within 4 weeks of randomization.
13. Treatment with other smoking cessation medications (bupropion, varenicline, nortriptyline, or any nicotine replacement therapy [NRT]) within 4 weeks of randomization or planned use of these other smoking cessation medications during the study.
14. Use within 2 weeks of randomization or planned use during the study of non-cigarette nicotine products (e-cigarettes, pipe tobacco, cigars, snuff, chewing tobacco, hookah) or marijuana vaping or smoking.
15. Any other reason that the investigator views the subject should not participate or would be unable to fulfill the requirements for the study.

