10.2.8. Questionnaires

The HADS, SBQ-R, Tobacco Craving and Alcohol Use questionnaires will be administered at [Section 8.6](#).

The HADS, SBQ-R and Tobacco Craving questionnaires will be summarized using descriptive statistics. For each questionnaire score, the actual value, change from baseline and percent change from baseline will be summarized by treatment arm and visit. Only subjects with non-missing results at both baseline and the post-baseline visit will be summarized at each time point.

The individual items on the Alcohol Use questionnaire will be summarized categorically by treatment arm and visit.

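### The SBQ-R total and its trigger of 7 are insensitive to new suicidal ideation on study and mix it with history; item-level change should be captured and reported as safety data

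*Protocol*

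**What the plan says.** Protocol Appendix 1 gives the SBQ-R at screening, Day 27 and Week 8. The two later administrations are "to monitor for any potential suicidal ideation or behaviour during the study as a safety parameter". On study, "An SBQ-R score ≥ 7 will be used to identify at-risk individuals who will need immediate evaluation by site personnel". The same threshold is the screening exclusion (Protocol 8.2, criterion 8). The appendix then adds, with no score attached: "Any potential suicidal ideation or behavior will be considered an SAE".

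The printed items differ in the time they cover. Item 1 asks "Have you ever thought about or attempted to kill yourself", item 2 asks "How often have you thought about killing yourself in the past year", item 3 asks about ever having told someone, and item 4 asks how likely a future attempt is. The same four items are printed for all three administrations. Scoring details are left to the Procedure Manual.

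The SAP derives a total score for the SBQ-R (8.6). SAP 10.2.8, which sits under efficacy, plans: "For each questionnaire score, the actual value, change from baseline and percent change from baseline will be summarized by treatment arm and visit". The SBQ-R is not among the safety endpoints in SAP 4.2. The SAP text plans neither a count of subjects with a new response nor any item-level summary.

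**The concern.** A form meant to detect ideation arising during an eight-week study should separate what happened in those weeks from what happened before. This one does so only indirectly, by comparing two totals that are made up largely of lifetime and past-year answers. A threshold chosen to keep people out at screening is then reused on people who by design all score below it.

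At stake is the only structured suicidality measure in the protocol; the HADS as printed in Appendix 5 has no suicide item. Protocol 1.3 describes varenicline as developed in part from cytisine and lists mental-health warnings in its prescribing information. The same section also reports a large trial that found no significant increase in neuropsychiatric events. The setting therefore justifies careful capture of new ideation, but it is not evidence of a problem with this drug.

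**Working it through.** **Inputs (Protocol Appendix 1, as printed).** Item 1 scores 1–4, item 2 scores 1–5, item 3 scores 1–3 and item 4 scores 0–6. Options a and b are taken to share the printed number. The total is the sum of the four.

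- Lowest total: 1 + 1 + 1 + 0 = 3. Highest: 4 + 5 + 3 + 6 = 18.
- A total of 7 or more is excluded, so correctly enrolled subjects start at 3–6.
- The threshold of 7 is stated without a derivation, so there is no figure to reproduce.

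**Time covered.** The longest interval from the first screening visit to the Week 8 visit is 28 + 56 + 3 = 87 days. Item 2 covers 365 days, so at least 365 − 87 = 278 of them precede the screening form. Items 1 and 3 have no limit.

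**A first event in a subject with no history.** The event is told to nobody (item 3 = 1). On item 2, one occasion scores 2, two score 3, and three or four score 4.

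| New event | Item 4 = 0 | Item 4 = 1 | Item 4 = 2 |
|---|---|---|---|
| One thought | 2+2+1+0 = 5 | 6 | 7 |
| Two thoughts | 2+3+1+0 = 6 | 7 | 8 |
| Three thoughts | 2+4+1+0 = 7 | 8 | 9 |
| One plan | 3+2+1+0 = 6 | 7 | 8 |
| Two occasions with a plan | 3+3+1+0 = 7 | 8 | 9 |
| One attempt | 4+2+1+0 = 7 | 8 | 9 |

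Among all patterns with item 1 ≥ 2 and item 2 ≥ 2, exactly five total less than 7: 2-2-1-0 (5), and 2-2-1-1, 2-2-2-0, 2-3-1-0 and 3-2-1-0 (6 each).

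**History and new events give the same total.** An old plan with nothing new is 3+1+1+0 = 5. A first new thought is 2+2+1+0 = 5.

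**Change is poorly graded.**

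- Old plan (baseline 5, item 4 = 0): a new single thought and a new single plan both give 3+2+1+0 = 6, a change of +1, below 7.
- Old attempt (baseline 4+1+1+0 = 6): a new thought, plan or attempt each gives 4+2+1+0 = 7, a change of +1.
- Percent change can reverse severity. A first thought from 3 to 5 is 2/3 = +67%. A new attempt in a subject with an old one, from 6 to 7, is 1/6 = +17%.
- One past-year thought at screening may leave the 12-month window while one new thought enters it. Then 2-2-1-0 stays 2-2-1-0, and the change is 0.

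**A crossing without an event.** From 4+1+1+0 = 6, moving item 4 from 0 to 1 gives 7. Both options deny any likelihood of an attempt.

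**The case against.** A reader might infer that neither the score nor its change measures suicidality on study. The documents do not support that. Scores of 7 or more are excluded at entry and, if recall is consistent, items 1–3 cannot rise without something new after screening. A crossing of 7 therefore means a new event or a higher answer on item 4. The remedy below depends on that information being there.

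A reader might also infer that new plans generally go unflagged. From a baseline of no history, a plan stays below 7 only if it occurred once, was told to nobody and item 4 is 0. Nor does old history alone trigger evaluation: with consistent answers, only a higher item 4 takes such a subject to 7, and the result is an evaluation that can resolve it.

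Nor can one conclude that the by-arm safety result would be wrong in both directions. SAP 11 plans no statistical comparison of arms on safety, and fixed history is balanced by randomization on average and cancels in change from baseline. The default statistics in SAP 6.1 include the maximum, so a crossing of 7 would be visible. They would not show how many subjects crossed, which item moved, or a new event that stayed at 5 or 6.

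Other routes exist. Adverse events are asked about at every visit, the SAE sentence has no threshold, an independent monitor reviews SAEs (Protocol 15.1), and the Week 8 visit list (12.2.4) adds an assessment of change in ideation. The Day 27 list (12.2.3), at end of treatment, has no such addition. The trigger and the SAE sentence can also be read as two tiers, so a contradiction is not established. Finally, the Procedure Manual, which may say more about scoring, is not available, and the SAP table shells are redacted.

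**Conclusion.** The concern holds in a limited form. The total and its trigger of 7 are insensitive to a new thought and, in one narrow case, to a new plan, and the total mixes these with history. A first single undisclosed thought totals 5 or 6 when item 4 is 0 or 1; a single undisclosed plan totals 6 only when item 4 is 0; a new attempt always reaches 7. Change from screening remains informative but grades severity badly, and percent change does so worst.

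This rests on the item scores as printed, on one event counting as one occasion on item 2, and on consistent recall. The patterns are arithmetic examples; the documents give no basis for estimating how many subjects would be missed. The point is a worthwhile and cheap improvement to safety reporting and does not undermine the trial's primary analysis.

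**What to change.** - **SAP 10.2.8.** Derive a subject-level variable, new since screening: any higher response on item 1, 2 or 3 than at the first screening visit. Report the number of subjects by arm at Day 27 and Week 8 as safety data, alongside or in place of mean and percent change in the total. Item responses are already collected on the form.
- **Protocol Appendix 1 and the Day 27 visit list.** Record whether any reported thought or act occurred since the previous SBQ-R, to match the assessment of change already listed at Week 8. This catches the case in which an older thought leaves the 12-month window and the item scores do not move.
- **Appendix 1 wording.** Reconcile the score trigger with the SAE sentence so that sites know how they relate when a total is below 7 but an item reports ideation. No clinical rule is proposed here.

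The cost is one derived variable, one table and one added question at existing visits.
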